3.2.1.2. Treatment-Emergent Adverse Event (TEAE)

Any event reported on the eCRF that occurs on or after the initiation of IMP and through the follow-up contact (i.e., date of Visit 9) is considered treatment-emergent. Additionally, it is an Adverse Event which was reported to have started on Day 1 without an associated onset time is assumed to be treatment emergent.

3.2.2. Clinical Safety Laboratory Assessments

The clinical laboratory tests as listed in the protocol will be performed in accordance with the laboratory manual and the Schedule of Assessments ([Section 9.1](#)). All laboratory tests with values considered clinically significantly abnormal during participation in the trial should be repeated until the values return to normal or baseline or are no longer considered clinically significant by the investigator or medical monitor. If clinically significant values do not return to normal/baseline within a period of time judged reasonable by the investigator, the etiology should be identified, and the medical monitor notified.

3.2.2.1. Treatment-Emergent Laboratory Abnormality and Toxicity

A treatment-emergent laboratory abnormality is defined as value outside the normal range which occurs on or after the start of IMP and through the last follow up contact.

A treatment-emergent laboratory toxicity is defined as an increase of at least one toxicity grade ([Section 9.5](#)) from the baseline assessment at any post baseline visit which occurs after the first administration of IMP and through last follow up contact. If a laboratory assessment obtained on Day 1 has unknown collection times, it will be assumed to be an assessment prior to the initiation of IMP. If the relevant baseline assessments are missing for a given participant, then any post-baseline graded toxicity (i.e., at least Grade 1) is considered a treatment-emergent laboratory toxicity.

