11.	
Participants with any of the following abnormalities in clinical laboratory tests at the Screening Visit, as assessed by the central laboratory and confirmed by a single repeat measurement, if deemed necessary:
 
 
• AST or ALT <math>\geq 2 \times</math> ULN
 
• Total bilirubin <math>\geq 1.5 \times</math> ULN. If Gilbert's syndrome is suspected, total bilirubin <math>>1.5 \times</math> ULN is acceptable if the conjugated or direct bilirubin fraction is <math><20\%</math> of total bilirubin
 
• eGFR <math><60</math> mL/min/1.73 m^2 (as estimated by the CKD-EPI 2021 equation [Levey et al, 2009; Delgado et al, 2022]) and as reported by the central laboratory
 
• TSH <math><</math> LLN
 
• Hemoglobin <math><</math> LLN
 
• WBC count <math><</math> LLN or <math>></math>ULN
 
• Neutrophil count <math><</math> LLN or <math>></math>ULN
 
• Platelet count <math><</math> LLN or <math>></math>ULN
 

12.	
Any other abnormal safety findings unless, based on the investigator's judgment, the findings are not medically significant and would not impact the safety of the participant or the interpretation of the trial results. The medical monitor should be contacted to discuss individual cases, as needed.
 
Tests with abnormal results that are potentially exclusionary should be repeated to ensure reproducibility of the result before excluding a potential participant based on criteria provided in the protocol.

Prior or Concomitant Therapies	
13.	Use of prohibited medications prior to randomization within the required wash-out period or likely to require prohibited concomitant therapy during the trial (see Section 6.7 ).
Other	
14.	Female participants who are breastfeeding or who have a positive pregnancy test result prior to receiving IMP.
15.	
Any condition possibly affecting drug absorption, including bowel resections, bariatric weight loss surgery, or gastrectomy (this does not include gastric banding).
 
Considering or scheduled to undergo any surgical procedure during the trial.

16.	Any other condition that would preclude IMP administration (eg, difficulty swallowing) or trial participation (eg, poor venous access).
17.	Participants who are known to be allergic or hypersensitive to the IMP or any of its components.

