5.17.3. Clinical Laboratory Assessments

Descriptive summaries of selective (quantitative) clinical laboratory results and change from baseline will be presented by study visit.

Additionally, for hematology, blood chemistry, coagulation, and urinalysis parameters, toxicity grade will be determined for laboratory tests with toxicity grade specified in [Section 9.5](#). Shifts from baseline to greatest (worst) post-baseline laboratory grade will be presented. For parameters not graded as described above, laboratory values outside the normal range for each systematically collected hematology, blood chemistry, and urinalysis parameters defined in Protocol Section 10.2 will be identified using shift tables. Each subject's hematology, blood chemistry, and quantitative urinalysis values will be flagged as "low" (below the lower limit of normal/LLN), "normal" (within the normal range), or "high" (above the upper limit of normal/ULN) relative to the normal ranges of the central laboratory. Each subject's qualitative urinalysis values will be flagged as "normal" or "abnormal". Shifts from baseline to high/normal/low status for the hematology, blood chemistry, and urinalysis parameters will be presented to for the maximum post-baseline value and the minimum post-baseline value for each laboratory test. Shifts from baseline to normal/abnormal status for urinalysis parameters will be presented to the maximum post-baseline value and the minimum post-baseline value for each laboratory test.

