The number and percentage of participants who have post-baseline elevations in liver transaminase (alanine aminotransferase [ALT] or aspartate aminotransferase [AST]) or bilirubin abnormalities in relation to fold above the upper limit of normal will be summarized according to the Food and Drug Administration's Premarketing Clinical Evaluation on Drug-Induced Liver Injury Guidance for Industry ([FDA, 2009](#)). Abnormal hepatic laboratory values will be categorized and evaluated for any occurrence among all post-baseline assessments (where "and" in the bulleted list below indicates elevations occurring at the same visit). Within each laboratory parameter grouping, a participant may be counted once per elevation criteria using the worst-case result. That is, a participant with a worst-case ALT elevation $>5 \times$ the ULN would be counted once in the ALT $> 3 \times$ ULN category and once in the ALT $> 5 \times$ ULN category, regardless of how many ALT elevations the participant had that met the $> 5 \times$ ULN and $> 3 \times$ ULN elevation criteria.

- ALT and/or AST $> 3 \times$ ULN and total bilirubin > 1.5 or $2 \times$ ULN
- AST $> 3, 5, 10, 20 \times$ ULN
- ALT $> 3, 5, 10, 20 \times$ ULN
- Total bilirubin $> 1.5, 2 \times$ ULN
- Alkaline phosphatase (ALP) $> 1.5 \times$ ULN

In addition, a Hy's law plot, a shift plot showing liver safety panel tests over time (baseline vs. post-baseline), and distribution plots of ALT, AST, ALP, and bilirubin over time will be produced using the format recommended by the Food and Drug Administration (FDA)/Industry/Academia Safety Graphics working group (<https://www.ctspedia.org/do/view/CTSpedia/StatGraphHome>). The plots to be included are the scatter plot of maximum transaminase versus maximum bilirubin, the liver test safety panel over time, and the distribution of ALT by time. The distribution plots for AST, ALP, and bilirubin will use the same format as used for ALT.

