5.17.4. Vital Signs

Vital signs and corresponding changes from baseline will be summarized by position (if applicable), visit, and timepoint using descriptive statistics. Vital signs results, including orthostatic changes, will be listed.

Out of range vital signs occurring post study baseline will be summarized. For supine blood pressure and heart rate, only averages of duplicates will be used. If an average is not available, the single reading will be used for summary.

The following out-of-range criteria will be summarized for post study baseline assessments:

- Systolic Blood Pressure (Supine)
 - ≤ 90 mmHg
 - ≥ 140 mmHg
- Orthostatic Change in Systolic Blood Pressure
 - ≥ 20 mmHg decrease upon standing compared with supine position
- Diastolic Blood Pressure (Supine)
 - ≤ 60 mmHg
 - ≥ 90 mmHg
- Orthostatic Change in Diastolic Blood Pressure
 - ≥ 10 mmHg decrease upon standing compared with supine position
- Heart Rate
 - < 60 bpm
 - > 100 bpm
- Respiratory Rate
 - < 12 breaths/min
 - > 20 breaths/min
- Temperature
 - $< 36^{\circ}$ C
 - $> 38^{\circ}$ C
- Body weight
 - $\geq 7\%$ increase
 - $\geq 7\%$ decrease

5.17.5. 12-Lead Electrocardiograms

Single or triplicate 12-lead electrocardiograms (ECGs) will be obtained during the trial. Any values taken in triplicate will be averaged for analysis. ECGs and corresponding changes from baseline will be summarized by treatment group and visit using descriptive statistics.

The number and percentage of participants who experience any post-baseline occurrence of potentially clinically significant QTcF will be summarized by treatment group. These presentations will include QTcF values > 450 to ≤ 480 , > 480 to ≤ 500 , and > 500 msec; or changes of > 30 to ≤ 60 or > 60 msec.

Additionally, a distribution plot of QTcF over time may be produced using the format recommended by the FDA/Industry/Academia Safety Graphics working group (<https://www.ctspedia.org/do/view/CTSpedia/StatGraphHome>). The graph format to be used is the same graph provided for the distribution of ALT by time and treatment.

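### SAP 3.2.2.1 labels any out-of-range laboratory value after first dose treatment-emergent without reference to baseline, although the protocol admits some abnormal baselines

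*SAP*

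**What the plan says.** SAP 3.2.2.1 gives two definitions. For abnormality: "A treatment-emergent laboratory abnormality is defined as value outside the normal range which occurs on or after the start of IMP", running to the last follow-up contact. For toxicity, the event "is defined as an increase of at least one toxicity grade" relative to baseline, with a separate rule when baseline is missing. SAP 9.3 is also baseline-referenced for treatment-emergent suicidal ideation.

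Protocol 5.2 allows some abnormal values at entry. Exclusion 11 rejects ALT or AST only from 2×ULN upward. It sets a bilirubin limit of 1.5×ULN and then relaxes it in the sentence beginning "If Gilbert's syndrome is suspected, total bilirubin": higher values are accepted, with no cap, if the direct fraction is under 20%. Lipids, glucose, CPK, GGT, uric acid and ALP are measured (Protocol 10.2) but have no numeric entry limit. Exclusion 12 leaves other abnormal findings to the investigator's judgment of medical significance.

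SAP 5.17.3 plans change from baseline, low/normal/high shifts and grade shifts: "Shifts from baseline to greatest (worst) post-baseline laboratory grade will be presented". Its liver table is different: "Abnormal hepatic laboratory values will be categorized and evaluated for any occurrence among all post-baseline assessments". For vital signs, SAP 5.17.4 says: "The following out-of-range criteria will be summarized for post study baseline assessments". Neither count carries a baseline condition.

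**The concern.** A treatment-emergent label tells the reader that something appeared or worsened after dosing started. As written, the abnormality label is earned simply by being out of range. That differs from the toxicity rule in the same subsection, so one participant can be treatment-emergent under one rule and not the other with no change in the measurement.

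The stake is interpretive. SAP section 6 says the planned sample size will not be reached and efficacy becomes exploratory, so the safety tables will be read more closely. Counting stable abnormalities dilutes relative differences in new onset and adds variance. In a sparse liver table, one or two participants with long-standing raised bilirubin can alter a row.

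**Working it through.** The plan gives no figure to reproduce, so the first step applies its rules to example values.

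**1. ALT examples (multiples of ULN).** Grades follow SAP 9.5, which uses ULN only: grade 1 above 1 to 3, grade 2 above 3 to 5.

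| Baseline → post-dose | Abnormality (3.2.2.1 as written) | Toxicity (3.2.2.1) | Abnormality if baseline must be normal |
|---|---|---|---|
| 1.8 → 1.8 | yes | no (1 → 1) | no |
| 1.8 → 1.2 | yes | no (1 → 1) | no |
| 1.8 → 3.2 | yes | yes (1 → 2) | no |
| 0.9 → 1.2 | yes | yes (0 → 1) | yes |

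The first two rows show the defect: an unchanged value and an improving one are both labelled treatment-emergent. The third shows that a baseline-normal rule leaves worsening of an existing abnormality to the toxicity definition, which catches it here.

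**2. Size, with no drug effect (illustration).** The documents give no baseline abnormality rates, so the inputs are assumed: b = share abnormal at baseline, 5% to 20%; r = chance that such a person is abnormal again after dosing, 70% to 90%; e = chance of a new abnormality from a normal baseline, 5% to 10%.

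- As written: b·r + (1 − b)·e. Lowest: 0.05×0.7 + 0.95×0.05 = 0.0825. Highest: 0.20×0.9 + 0.80×0.10 = 0.26.
- Baseline required normal: (1 − b)·e, from 0.80×0.05 = 0.04 to 0.95×0.10 = 0.095.
- Share of flags that pre-existed: b·r divided by the as-written rate. Lowest: 0.035/0.13 = 27%. Highest: 0.18/0.22 = 82%.

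A simulation on other assumptions (95% reference range, one baseline and five post-dose draws, within-person correlation 0.5, 0.7 or 0.85) gives about 14%, 23% and 35%. If one in-range Screening value is also required, as for WBC, neutrophils and platelets, the shares fall to about 12%, 17% and 22%.

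**3. Effect on a comparison.** Take b = 10% and r = 90% in both arms, with e = 5% on placebo and 10% on darigabat.

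- As written: 0.09 + 0.90×0.05 = 13.5% versus 0.09 + 0.90×0.10 = 18.0%. Difference 4.5 points, ratio 18.0/13.5 = 1.33.
- Baseline required normal, as a share of all participants: 4.5% versus 9.0%. Difference 4.5 points, ratio 2.0.
- Summing p(1 − p) over the arms gives 0.135×0.865 + 0.18×0.82 = 0.264 as written, against 0.045×0.955 + 0.09×0.91 = 0.125. The standard error of the difference is √(0.264/0.125) ≈ 1.45 times larger as written.

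The expected absolute difference is unchanged. The ratio is diluted and precision is lost.

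**4. Liver table.** A suspected Gilbert's participant with bilirubin 1.8×ULN before and after dosing stays in grade 2 in the shift table but is counted in the above-1.5×ULN bilirubin row. A baseline ALP above 1.5×ULN is counted likewise. If that participant's ALT rises from 0.9 to 3.2×ULN at the same visit, the combined row is met although only ALT moved. A rule counting those newly meeting the combined criterion would still count this person, because the combination was absent at baseline.

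**5. Vital signs.** The table counts heart rate below 60, while exclusion 10 rejects only below 45 or above 100. It counts supine systolic ≤90 and diastolic ≤60, for which exclusion 10 sets no lower limit. The high blood-pressure cut-offs (140 and 90) coincide with exclusions, so the gap is mainly on the low side. Assuming mean heart rate 70, between-person SD 8, within-person SD 6 and four post-dose visits, about 34% are flagged, 38% of them already below 60 at baseline; new onset is 25% among those at risk.

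**The case against.** The strongest reply is that the defect may have no output. No analysis in the SAP text uses the term. The laboratory outputs in 5.17.3 are changes and shifts from baseline, plus a baseline-versus-post-baseline liver plot. The shells are a separate document and cannot be checked here. Out-of-range results become adverse events only when judged clinically significant (Protocol 10.3.1). All of this stands, and it confines the point about 3.2.2.1 to a definition.

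A reader might infer that pre-existing abnormalities will be reported as drug effects. The documents do not support that: with randomisation and a placebo arm the added background is expected equally in both groups. A reader might also infer that the liver table will manufacture Hy's law cases. That goes too far. ALT and AST must be below 2×ULN at Screening, so the combined row's cut-off of 3×ULN generally reflects a real transaminase rise, and Protocol 10.6.2 requires that no alternative cause explains a potential case. What remains is that the row does not show whether bilirubin was already high.

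The liver and vital-sign counts are described as post-baseline, not treatment-emergent, so they do not breach the SAP's own definition. That is fair; for those tables the point is an improvement in presentation. Nor are most analytes unrestricted at entry: key hematology values are limited at Screening and exclusion 12 applies to the rest. Hence the wording here is no numeric limit, not no limit.

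**Conclusion.** The point holds as a defect of definition with a modest extension to two planned tables. SAP 3.2.2.1 would label unchanged or improving pre-existing values treatment-emergent wherever the term is applied, inconsistently with the toxicity rule beside it. The consequence is added background in both arms, which dilutes relative differences in new onset and costs precision. It is not a false drug effect, and the efficacy analyses are untouched.

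The size is not known. The 27% to 82% range, the 14% to 35% simulation results and the heart-rate figures all rest on assumed rates, correlations and variances. They show that the share could be material, not what it will be. Equal background across arms assumes balanced baselines and that treatment does not change how long an existing abnormality persists.

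**What to change.** - **SAP 3.2.2.1.** Require that the baseline value was normal, out of range in the other direction, or missing. Alternatively, delete the term and rely on the shift tables and the toxicity definition. If the term stays, check that the shells apply it this way.
- **SAP 5.17.3, single-analyte bilirubin and ALP rows, and the out-of-range table in 5.17.4.** Keep the any-occurrence count. Add the number newly meeting each criterion among those not meeting it at baseline, and list baseline-positive participants separately.
- **SAP 5.17.3, combined ALT/AST-and-bilirubin row.** Leave the count as it is. Flag participants whose bilirubin already exceeded the cut-off at baseline and show their direct bilirubin, which Protocol 10.2 already collects.

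The cost is one clause, extra columns in two tables and a flag, with no new data. Denominators for the new-onset counts will differ by criterion and should be printed in each row.

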3.2.3. Columbia-Suicide Severity Rating Scale

Suicidality will be monitored during the trial using the Columbia-Suicide Severity Rating Scale (C-SSRS). It was designed to quantify the severity of suicidal ideation and behavior.

This trial will use the “Baseline/Screening” and “Since Last Visit” versions of the scale. The “Baseline/Screening” version, which assesses the lifetime experience of the participant with suicide events and suicidal ideation and the occurrence of suicide events or ideation within a specified time period prior to entry into the trial, will be completed for all participants at screening to determine eligibility and confirmed at baseline.

The “Since Last Visit” C-SSRS form will be completed at all visits after screening and baseline. The investigator will review the results of the “Since Last Visit” C-SSRS during the trial to determine whether it is safe for the participant to continue in the trial. If a participant demonstrates potential suicidal ideation associated with actual intent or method or plan as indicated by “YES” answers on item 4 or 5 of the C-SSRS, the investigator will evaluate whether a risk assessment by a qualified mental health professional (or the investigator alone if the investigator is a qualified mental health professional) is needed and whether the participant should continue in or be discontinued from the trial.

Details of C-SSRS categories as well as definition of treatment emergent events are provided in [Section 9.3](#).

3.2.4. Vital Signs

Vital signs include systolic and diastolic blood pressures, heart rate, respiratory rate, and body temperature. At the Screening Visit, triplicate blood pressure and heart rate measurements will be obtained after the participant has been supine and at rest for at least 3 minutes. Measurements will be obtained at approximately 1-minute intervals at the time points indicated in the Schedule of Assessments ([Section 9.1](#)).

Duplicate supine heart rate and blood pressure measurements will be taken at all other time points. The values will be individually recorded, and the values will be averaged by the sponsor for all time point assessments following confirmation of eligibility. For determination of eligibility, the average of the last 2 values will be used.

The supine heart rate and blood pressure measurements will be followed by a single measurement after approximately 2 minutes in a standing position to allow for orthostatic assessments.

3.2.5. Electrocardiograms

At Screening, triplicate 12-lead electrocardiograms (ECGs) are required to assess participant eligibility. A triplicate set of ECGs is 3 consecutive ECGs collected 1 to 2 minutes apart over a 5-minute period. The central ECG service will provide the QTcF corrections and average of the 3 ECGs performed to determine eligibility. At all other specified time points in the Schedule of Assessments where an ECG recording must be performed, only a single ECG is required.

All ECG recordings will be obtained after the participant has been supine and at rest for approximately 3 minutes. Additional 12-lead ECGs may be obtained at the investigator's discretion and should always be obtained in the event of an early termination. The ECG will be repeated if any results are considered to be clinically significant. Any clinically significant changes occurring during the trial will be recorded in the AE section of the eCRF.

3.2.6. Prior and Concomitant Medications

Prior medications are those medications taken prior to and ended prior to the initiation of IMP. Concomitant medications are those medications taken on or after the initiation of IMP. These medications include those medications started before the initiation of IMP and continuing post Day 1. These medications will be recorded in the PRIOR AND CONCOMITANT MEDICATIONS eCRF. Medications that start after the last dose of IMP will be classified as taken post last dose and will not be considered as concomitant.

3.2.7. Prior and Concomitant Non-Drug Therapy/Procedures

Prior non-drug therapy/procedures are those medications taken prior to and ended prior to the initiation of IMP. Concomitant non-drug therapy/procedures are those non-drug therapy/procedures taken on or after the initiation of IMP. These therapy/procedures include those non-drug therapy/procedures started before the initiation of IMP and continuing post Day 1. The investigator will record all therapies (including vaccines, over the counter or prescription medicines, vitamins, and/or herbal supplements) taken by the participant from 30 days prior to signing the ICF through the end of the evaluation period (defined as the time period during which participants are evaluated for primary and/or secondary objectives). These non-drug therapy/procedures will be recorded in the NON-DRUG THERAPY/PROCEDURES eCRF.

3.2.8. Physical/Neurological Examinations

The full physical examination will include a review of the following body systems: head, ears, eyes, nose, mouth, skin, heart and lung examinations, lymph nodes, gastrointestinal, and musculoskeletal systems.

The limited physical examinations will include evaluation of cardiovascular, pulmonary, and gastrointestinal systems.

A full neurological examination will include an assessment of the participant's mental status (level of consciousness, orientation, speech, memory, etc.), cranial nerves, motor (muscle appearance, tone, strength, and reflexes), sensation (including Romberg sign), coordination, and gait.

Any condition present at the post-treatment physical and neurological examinations that was not present at the baseline examination should be documented as an AE and followed to a satisfactory conclusion.

